7.2 Serious and unexpected adverse events

All serious adverse events must be reported promptly to the Sponsor and in any case not later than 24 hours after their occurrence. The report must be made by telephone or fax to the following contact at the following numbers:

[name]

Akos Limited

[contact]

[contact]

The Investigator must also complete a serious adverse event form and transfer it to Akos Limited as soon as is possible.

Akos Limited will report all serious, related and unexpected adverse events to the MHRA within 7 days of being notified by the investigator.

7.3 Withdrawals due to adverse events.

Any study subject may be withdrawn from the study at any time at the discretion of the investigator or the request of the subject (see section 4.2.3). The reason for doing so must be clearly documented in the CRF and, if the withdrawal is due to an adverse event, the pertinent page of the CRF must be completed. The Investigator should use his best efforts to follow up the subject following withdrawal from the trial and the appropriate follow up portion of the CRF should be completed at that time.

In general, subjects withdrawn early from the study will be replaced. If withdrawal is caused by an adverse event, which the Investigator considers may be related to the study compound, the subject will not be replaced without reference to the ethics committee responsible for the study.

In the event of any abnormalities considered to be clinically significant by the investigating physician, subjects will be followed up with appropriate medical management until values are considered to be clinically acceptable. Referral or collaborative care will be organised if considered necessary.

8. DATA MANAGEMENT AND STATISTICAL ANALYSES

8.1 Rationale for sample size

The sample size for this protocol was estimated using unpublished data provided by the Chief Investigator from a within-subject reproducibility nasal allergen challenge study, with no drug intervention, on 8 subjects. For these subjects the within-subject variability was greater for levels of IL-4 in nasal filter paper, than for levels of IL-5 and IL-13. The area under the response curve for IL-4 from 1 to 8 hours post nasal allergen challenge (AUC(1-8)) had a standard deviation of within-subject differences

(SD) which was 13.4% of the mean AUC(1-8). These data also suggest a similar relationship between mean response and SD for the maximum IL-4 level from 1 to 8 hours post nasal allergen challenge (Max(1-8)).

In view of the small size of the unpublished data set and the need to incorporate additional within-subject variability introduced by the effects of OC000459, it was felt prudent to double the estimate of SD in the sample sizing for this protocol. With this assumption and using a 5% significance level, 16 subjects is the requirement for a crossover study to achieve >90% power of detecting a 25% reduction in AUC.

In this protocol, the period of observation is extended to 9 hours post nasal allergen challenge, rather than the 8 hours used in the unpublished data used for sample sizing. It is anticipated that the relationship between response and within-subject variability for AUC and Max will not be substantially affected by this change.

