There is strong evidence that allergen-reactive type 2 T helper (Th2) cells play an important role in the induction and maintenance of the allergic inflammatory cascade¹⁴. Cytokines and chemokines produced by Th2 cells (IL-4, IL-5, IL-6, and IL-13) may be pivotal to the pathophysiology of allergic disorders: involving production of IgE; recruitment and activation of mast cells and eosinophils; mucus hypersecretion; subepithelial fibrosis; and tissue remodelling. Several studies have demonstrated significant expression of various cytokines and chemokines in inflammatory cells at sites of nasal allergic inflammation¹⁵⁻¹⁹. Excessive production of IL-5 and IL-13, may be critical to the allergic response^{14,20}.

Maintenance treatment with topical steroids exerts a range of anti-inflammatory nasal effects on production of eotaxin²¹, RANTES, MIP-1 α , IL-8, IL-1 β ¹⁷, TNF- α ²² and IL-5²³. Topical allergen challenge increases the levels of mucosal mRNA of IL-5 and IL-13^{19,23} but nasal cytokines and chemokines may be produced at low concentration in nasal secretions, and may be undetectable when employing conventional ELISAs. A single dose of topical corticosteroid has been shown to reduce levels of GM-CSF and IL-5 detected by absorption with filter paper following nasal challenge with grass pollen in allergic rhinitis^{23,24}.

In order to sample nasal exudates for allergic inflammatory mediators, the classical methods of nasal lavage are those described by Naclerio et al.²⁵, the nasal pool method of Greiff et al.²⁶, and the use of a Foley's catheter by Grünberg and colleagues²⁷. Lavage is performed with saline with volumes between 1 and 10ml of lavage fluid. The repeatability and validity of different nasal lavage methods have been compared²⁸. An important demonstration of the utility of this methodology for assessing therapy was the demonstration that pre-treatment with topical corticosteroids causes inhibition of release of histamine, kinins and symptoms after NAC²⁹. Peptidyl leukotrienes are also released³⁰ and there is a later increase in histamine during the late nasal reaction³¹. More recently, increases in IL-5 and eotaxin have been detected in nasal lavage fluid in the early and late reactions following NAC^{21,32}.

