3.2 Safety and biological activity endpoints

Biological activity will be assessed as follows:

Primary endpoint:

Levels (AUC and maximum concentration) of IL-4, IL-5 and IL-13 in nasal filter paper (measured using Luminex) after nasal allergen challenge.

Secondary endpoints:

Total eosinophil counts in nasal lavage fluid, PGD₂ concentrations in filter paper after nasal allergen challenge.

Total nasal symptom scores after nasal allergen challenge.

Adverse events, vital signs, concomitant medication and laboratory safety parameters.

Plasma drug concentrations will be related to IL4, 5 and 13, PGD₂ and eosinophil levels in nasal secretions.

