8.2 Statistical analysis

The primary objective of the study is to assess the effects of OC000459 on levels of IL-4, IL-5 and IL-13 (Th2 cytokines) in nasal filter paper after nasal allergen challenge (NAC). The primary analyses of these effects will be based on the area under the curve of these levels from 1 to 9 hours after NAC (AUC(1-9)) and the maximum level from 1 to 9 hours after NAC (Max(1-9)). These measures of response will be analysed using a two-way crossover analysis with treatment and period as factors and investigating OC000459 versus placebo differences. In addition the IL-4, IL-5 and IL-13 response profiles for OC000459 and placebo will be summarised and compared at each time-point pre-NAC and over the 9 hour period after NAC.

Similar approaches will be used for the analysis and summary of the secondary measures, including Th2 cytokines at 15 and 30 min after NAC, eosinophil counts in nasal lavage fluid, PGD2 levels in nasal filter paper, and total nasal symptoms scores.

After all data have been collected, the top copy of each CRF page will be sent to the data entry and analysis unit of Arros Limited. The bottom copy of the CRF pages will be retained by the investigator.

The relationship between plasma concentrations of OC000459 and the above measures of effect will also be summarised.

In addition, further exploratory analyses will be carried out to fully assess the effects of OC000459.

A randomised code will be prepared by an independent consultant statistician. Subject disposition, demographic and baseline data will be summarised by sequence group and overall. Adverse events, concomitant medication, vital signs and laboratory safety findings will be summarised by treatment group. All safety data will be listed.

Further detail of the statistical analyses and data presentations to be used in reporting the study will be provided in a Statistical Analysis Plan which will be finalised prior to breaking the blind.

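### Does one 5% level and one >90% power figure leave the six unranked primary comparisons (AUC and Max of three cytokines) wrongly specified?

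*Protocol*

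**What the plan says.** Protocol section 3.2 gives the primary endpoint as "Levels (AUC and maximum concentration) of IL-4, IL-5 and IL-13 in nasal filter paper (measured using Luminex) after nasal allergen challenge". Section 8.2 bases the primary analyses on the area under the curve and the maximum, both from 1 to 9 hours after challenge, for each of the three cytokines. Each is analysed as a two-way crossover with treatment and period as factors. That makes 3 × 2 = 6 primary comparisons. None is named as lead, and no rule says whether one, some or all must succeed.

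Section 8.1 supplies one sizing calculation. It takes the SD of within-subject differences for IL-4 AUC(1-8), 13.4% of the mean, from a reproducibility study in 8 subjects. Of that SD it says "it was felt prudent to double the estimate of SD in the sample sizing for this protocol". It concludes: "16 subjects is the requirement for a crossover study to achieve >90% power of detecting a 25% reduction in AUC". It also records that "the within-subject variability was greater for levels of IL-4 in nasal filter paper, than for levels of IL-5 and IL-13", and that the IL-4 maximum shows a similar relation between mean and SD.

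Section 8.2 closes by leaving further analysis detail to an SAP that is finalised before the blind is broken.

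**The concern.** Six comparisons are labelled primary, yet the 5% level and the >90% power are worked out for one. A reader could take both figures as properties of the trial's primary result as a whole, which they are not.

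Two things could go wrong. If each comparison were tested at an unadjusted 5% and any success were reported as a positive primary result, the chance of a false positive would exceed the nominal rate. If success required all six, the chance of achieving it would fall below the stated 90%. Section 3.3 calls this the first proof-of-concept study of the compound, so the reading of its primary result is likely to influence later development.

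**Working it through.** **Inputs (section 8.1 unless stated).** Effect 25% of the mean. SD of within-subject differences 2 × 13.4% = 26.8%. Significance level 5%; sidedness is not stated and two-sided is assumed. N = 16 completers (also section 4.1). The section 8.2 model has treatment and period, so residual df = 16 − 2 = 14.

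**1. The plan's own figure.** Noncentrality = (25/26.8) × √16 = 3.73. The critical value of t on 14 df at two-sided 5% is 2.145, so power is 93.4%. With N = 14 (df 12) the noncentrality is 3.49 and power is 89.3%. Sixteen is therefore the smallest balanced size that exceeds 90% for one comparison, and the statement in 8.1 reproduces.

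**2. Does the figure carry over to each of the six?** IL-5 and IL-13 are said to vary less than IL-4, and IL-4 Max is said to behave like IL-4 AUC. For illustration, an SD of 0.75 × 26.8% = 20.1% (assumed ratio) gives noncentrality 4.98 and power 99.6%. So >90% is a fair statement of marginal power for each comparison at an unadjusted 5%.

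**3. The set of six under different rules.** With independent endpoints, the chance of at least one false positive is 1 − 0.95^6 = 26.5% two-sided, or 1 − 0.975^6 = 14.1% in the direction of benefit. All-six power with equal SDs is 0.934^6 = 66%. For correlated endpoints, 8 + 8 crossovers with six normal outcomes and period-adjusted t tests on 14 df were simulated. The correlations are assumed (between cytokines / between AUC and Max).

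| Correlations | Any of six, unadjusted 5%: two-sided error | Same, benefit direction | All six: power, equal SDs | All six: power, IL-5/IL-13 SD ratio 0.75 | At least one of six, Holm or Bonferroni: power, equal SDs |
|---|---|---|---|---|---|
| 0 / 0 | 26% | 14% | 66% | 86% | >99% |
| 0.3 / 0.7 | 22.5% | 11% | 74% | 88% | 99% |
| 0.5 / 0.9 | 18% | 9% | 80% | 90% | 96% |
| 0.7 / 0.9 | 16% | 8% | 82% | 91% | 93% |
| 0.9 / 0.9 | 12% | 6% | 86% | 91% | 88% |

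The first row is not realistic. AUC and Max of a cytokine come from the same nine hourly samples, from 1 to 9 hours. Even if those nine values were independent normal variables, the AUC-Max correlation would be about 0.55. The benefit-direction column is the relevant one for a claim that the drug works, and its nominal rate is 2.5%.

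**4. What each possible rule costs.** Bonferroni at 0.05/6 has critical value 3.07, and power for a given comparison falls to 73%. A fixed order led by IL-4 keeps 93.4% for the first test. If IL-4 did not respond while IL-5 and IL-13 fell by 25%, that order would allow a claim of benefit in only 2.5% of trials, against 86% to >99% for at least one success under Holm. This matters because section 1 says of the other two cytokines: "Excessive production of IL-5 and IL-13, may be critical to the allergic response".

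**5. The cushion in the SD.** At the observed, undoubled 13.4%, noncentrality is (25/13.4) × 4 = 7.46, and power at 0.05/6 exceeds 99.9% for each comparison. The power losses above exist only within the deliberately doubled SD. The error rates do not depend on the SD.

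**The case for a change.** The strongest case for a change is that the mismatch lies within the protocol and is not merely detail awaiting an SAP. The protocol chose both its primary set and its sizing basis. It wrote "With this assumption and using a 5% significance level, 16 subjects is the requirement for a crossover study" without saying that this level and the power belong to one comparison in six. Under any plausible correlation, an unadjusted any-of-six reading would at least double the nominal error rate. Neither the doubled SD nor the choice of the noisiest cytokine corrects that. Wording would cost no subjects.

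Part of this stands. The arithmetic for the set is right, the >90% does not describe the set, and the protocol alone does not tell a reader what counts as success. It does not show that any stated figure or rule is wrong. Section 8.1 names AUC as the quantity its power refers to, and explains through IL-4 variability and the remark on Max why the other endpoints are covered. The harmful rules are supplied by the reader; the protocol states neither. The success rule and any adjustment are commonly settled in the SAP, which section 8.2 promises before unblinding and which was not available here.

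**Conclusion.** No change to the plan follows. The sizing statement is correct (93.4% against >90% claimed) and is best read as marginal power for each comparison at an unadjusted two-sided 5%.

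The possible harm is conditional. An unadjusted any-of-six rule would give roughly 6% to 11% false claims of benefit against 2.5%. An all-six rule would have power of about 74% to 86% with equal SDs, or 88% to 91% if IL-5 and IL-13 had 0.75 of the IL-4 SD. These ranges leave out the zero-correlation case and rest on assumed correlations and an assumed SD ratio, neither of which the protocol gives.

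What is missing is a success rule, which the scheduled SAP can state. A fixed order, an adjustment across all six and separate reporting each give something up in a 16-subject proof-of-concept study, so the protocol is not at fault for leaving that choice open.

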8.2 Statistical analysis

The primary objective of the study is to assess the effects of OC000459 on levels of IL-4, IL-5 and IL-13 (Th2 cytokines) in nasal filter paper after nasal allergen challenge (NAC). The primary analyses of these effects will be based on the area under the curve of these levels from 1 to 9 hours after NAC (AUC(1-9)) and the maximum level from 1 to 9 hours after NAC (Max(1-9)). These measures of response will be analysed using a two-way crossover analysis with treatment and period as factors and investigating OC000459 versus placebo differences. In addition the IL-4, IL-5 and IL-13 response profiles for OC000459 and placebo will be summarised and compared at each time-point pre-NAC and over the 9 hour period after NAC.

Similar approaches will be used for the analysis and summary of the secondary measures, including Th2 cytokines at 15 and 30 min after NAC, eosinophil counts in nasal lavage fluid, PGD2 levels in nasal filter paper, and total nasal symptoms scores.

After all data have been collected, the top copy of each CRF page will be sent to the data entry and analysis unit of Arros Limited. The bottom copy of the CRF pages will be retained by the investigator.

The relationship between plasma concentrations of OC000459 and the above measures of effect will also be summarised.

In addition, further exploratory analyses will be carried out to fully assess the effects of OC000459.

A randomised code will be prepared by an independent consultant statistician. Subject disposition, demographic and baseline data will be summarised by sequence group and overall. Adverse events, concomitant medication, vital signs and laboratory safety findings will be summarised by treatment group. All safety data will be listed.

Further detail of the statistical analyses and data presentations to be used in reporting the study will be provided in a Statistical Analysis Plan which will be finalised prior to breaking the blind.

8.3 Criteria for eligibility of subject data

In order to be evaluable, subjects must have given written informed consent, complied with all the entry criteria and the dosing regimen and have completed 90% of all protocol driven measurements. Those who do not will be considered to be major protocol violations in the biological activity analyses.

All subjects, including those who drop out for any reason and those not compliant with the protocol and who receive OC000459/placebo will be evaluated for safety. Subjects not evaluable for safety for whatever reason will be identified in the safety data listings.

The safety population will consist of all subjects who received at least one dose of study medication.

8.4 Case report forms (CRFs)

Data must be entered onto the case report forms completely, legibly and in timely fashion by the investigator his/her designees. The Investigator will also verify that all the data contained on these forms are accurate and will sign the forms once they are completed. Where source data are available, these will be checked against the data in the CRF.

CRFs always remain the property of the Sponsor and must be available for review and retrieval by Sponsor staff at any time. Investigators are requested to enter data promptly onto CRFs in order to facilitate review, monitoring and correction of CRFs in a timely fashion.

Any subsequent alterations to the data must be made by striking out the previous entry with a single line and by writing the new value next to it. All such changes must be initialled and dated by the individual completing the CRF. Whiting or scribbling out of errors is not acceptable.

When the monitor reviews the CRFs, certain queries may arise. These will be documented in writing and the resolution will also be noted in writing. Copies of these query resolution forms will be kept in both the Investigator's and the Sponsor's archive.

Once CRFs have been completed, the top copy of each CRF page will be collected for data entry and analysis at Akos Limited. The bottom copy of the CRF page will be retained at the investigator site. At the end of the study all original CRF pages will be returned to the Sponsor for archiving. The Investigator will retain all CRFs and other study related documents in a secure but accessible place.

8.5 Double blind codes

A randomised code list will be prepared by an independent consultant statistician ([name], TLwise Consulting Ltd, [contact]) using an industry standard computer package and will be provided to Penn Pharmaceutical Services. As well as providing the already packaged and labelled clinical study medication to the pharmacy at the Royal Brompton Hospital, Penn Pharmaceutical Services will also supply the Clinical Studies Unit with individual envelopes for each subject containing the sequence code which identifies the order of study medication in the two Treatment Periods [Group A (OC000459 followed by placebo) or Group B (placebo followed by OC000459)] before the trial starts. These must be held in a secure place within the CSU. The double blind code must not be broken except in the case of severe and serious adverse events where knowledge of the subject's study medication would be of benefit to therapy. The Medical Monitor must be contacted immediately by the investigator for a discussion of the circumstances if a code break is deemed necessary. If a code is broken, the time, date and reason and the name of the person breaking the code must be recorded in the CRF and on the envelope.

The Medical Monitor will also provide a list of all members, their affiliations and the written procedures if requested to the Sponsor in confidence.

8.6 Criteria for early termination of the trial

The trial may be terminated early if suspected unexpected serious adverse reactions (SUSARs) occur in any of the healthy subjects (see section 5.7). If this occurs, the Principal Investigator will discuss next steps with the Sponsor and the Medical Monitor.

9. ETHICAL CONSIDERATIONS

9.1 Subject information sheets and consent forms

All subjects invited to participate in a clinical trial are entitled to make their decision based on the fullest amount of information available at the time. In order to make that choice, they will be given a written document in English expressed in clear concise lay language to consider. The document will previously have been approved by the Main REC and may be updated as new important information becomes available that would affect a subject's willingness to participate or continue in the trial.

This document will tell potential subjects about the nature of the indication and the drug, its efficacy and safety profile in animals and man, the human experience to date and the route of administration. It will also outline the numbers of subjects in the trial and the steps of the protocol as they will apply to the individual including number of visits, number of procedures including venepunctures and types of measurements to be performed so that the individual has a clear picture of the risks, inconveniences and benefits that may accrue from the trial. If subjects are to be reimbursed expenses, the sums involved must be made known.

The individual must be made aware that he may refuse to join the trial or may withdraw at any time without prejudicing further medical care and that he is covered by the Sponsor's indemnity insurance in the event of a trial related injury. A contact with whom suspected trial related injuries may be discussed must be given. Individuals must also know that their personal medical records may be reviewed in confidence by the Sponsor's staff or representatives and by Regulatory Authorities and Ethics Committees from time to time and that personal information about them will be held on a confidential database. Conditions for ensuring the anonymity of the data and the security and confidentiality of the database should be explained.

Consent will always be given in writing after the subject has had adequate time to reflect on the information and to ask further questions if need be. The subject will sign and date the consent form.

9.2 Main Research Ethics Committee review.

Main RECs will conform to the standards of ICH E6. They will be provided with the appropriate COREC form, copies of the protocol, any amendments, subject information and consent forms, subject recruitment procedures, details of payments to subjects (where relevant), the Investigator Brochure, the Investigator's Curriculum Vitae and Clinical Trial Indemnity Insurance Documents (if requested) for review. Approval will always be given in writing and within a reasonable timeframe. The approval documents should clearly identify the protocol by title and Sponsor's number, identify the committee members present when the approval was granted and list any required amendments with the reasons for them. If a protocol is refused approval, the reasons will be given in writing. Refusals will be notified to the MHRA.

No trial may begin and clinical trial supplies will not be shipped until written approval is received by the Sponsor. The Main REC will also provide a list of its members, their affiliations and its written procedures if requested to the Sponsor in confidence

as part of the pre study documentation. The Main REC must keep records of all its procedures and decisions for at least three years after completion of the trial and make them available on request to representatives of regulatory authorities.

